All histological assessments were performed by two independent pathologists blinded to treatment allocation. Inter-observer agreement was assessed using Cohen's kappa coefficient.

- ii. Time to achieve complete wound closure - the time to achieve complete wound closure (defined as 100% epithelialization with no drainage) of the target ulcer by the end of 6 weeks [Time Frame: 6 weeks]
- iii. Proportion of subjects to obtain complete closure - the proportion of subjects that obtain complete closure over the 6-week treatment period [Time Frame: 6 Weeks]
- iv. Mean number of repeated application - mean number of repeated applications of the Advanced Skin Substitute & Human Amnion/Chorion Membrane used to obtain wound closure [Time Frame: 6 Weeks]
- v. Incidence of adverse events - incidence of adverse events related to the intervention (e.g., infection, allergic reactions) [Time Frame: 6 Weeks]

Other Pre-specified Outcome Measures:

- i. Change in Pain - change in pain measured by a Visual Analog Scale with score range from 0 to 10, wherein 0="no pain" to 10="severe pain" [Time Frame: 7 weeks including 1-week follow-up]. Pain scores were assessed weekly.
- ii. Change in quality of life - change in quality of life assessed using the Wound-QoL questionnaire measured as 'not at all', 'a little', 'moderately', 'quite a lot' and 'very much' for 17 questions [Time Frame: 7 weeks including 1-week follow-up]
- iii. Healed Wound appearance assessment using Manchester Scar Scale - the resultant new skin is assessed and documented at each visit using the Manchester Scar Scale assessing colour, finish, contour, distortion & texture with values given from 1 to 4 wherein 1 denotes excellent and 4 means poor [Time Frame: 7 weeks including 1-week follow-up]

Data Collection and Monitoring

- a. Baseline data: Demographics, medical history, ulcer characteristics.
- b. Weekly follow-ups: Wound measurements (photographic documentation), assess healing progress, pain scores, record adverse events and patient-reported outcomes.
- c. Histopathological specimens were obtained at baseline and day 5 for vascularity assessment.
- d. End-of-Study Visit (Week 6): final wound assessment, collect patient feedback on treatment experience, quality of life and scar assessment.
- e. Data entry and monitoring was managed using an electronic data capture system.

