- e. Data entry and monitoring was managed using an electronic data capture system.

Data Analysis: Data was analysed using SPSS v26.0. Continuous variables were expressed as mean \pm standard deviation, and categorical variables as frequencies and percentages. Student's t-test was used for comparing continuous variables between groups, and chi-square test for categorical variables. A p-value <0.05 was considered statistically significant. Kaplan-Meier survival analysis was used to assess time to complete healing and Cohen's d values for primary histopathological parameters.

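### The Manchester Scar Scale score is not tied to the date of closure, so scar age and the set of ulcers rated can differ between arms; report it descriptively at a fixed interval after closure

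*Protocol*

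**What the plan says.** The Protocol, under Other Pre-specified Outcome Measures, item iii, is titled "Healed Wound appearance assessment using Manchester Scar Scale". It states that "the resultant new skin is assessed and documented at each visit using the Manchester Scar Scale". Five aspects of appearance are each rated from 1 (best) to 4 (worst). The window is "Time Frame: 7 weeks including 1-week follow-up".

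Data Collection and Monitoring, in both documents, gives a different schedule. Item b lists "Weekly follow-ups: Wound measurements (photographic documentation), assess healing progress, pain scores, record adverse events and patient-reported outcomes", without scar assessment. Item d places it at the final visit: "End-of-Study Visit (Week 6): final wound assessment, collect patient feedback on treatment experience, quality of life and scar assessment".

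Complete closure, in the Protocol's secondary outcome ii, is "defined as 100% epithelialization with no drainage) of the target ulcer by the end of 6 weeks", so an ulcer may reach it at any weekly visit in that period.

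The SAP's Data Analysis section has no analysis specific to the scar score. It has only the general rules: "Student's t-test was used for comparing continuous variables between groups", and chi-square for categorical variables. Neither document names the visit analysed, the interval since closure, or what is done with an ulcer that is not fully closed.

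**The concern.** Two things other than scar quality can move a between-arm comparison of these scores.

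- **Scar age.** At any one calendar visit, ulcers that closed early carry older skin than ulcers that closed late. If one product closes ulcers sooner, its scars are on average older when rated.
- **Selection.** An ulcer must have healed before its healed appearance can be rated. Healing follows randomisation and is expected to differ by arm, so the rated patients in the two arms are no longer randomised groups. The arm that heals more ulcers also contributes more of the hard-to-heal ones.

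If appearance improves as skin matures, the two influences pull in opposite directions. A difference, or the lack of one, could then not be read as an effect of the product on the quality of healed skin. What is at stake is the interpretation of one exploratory-level outcome. The primary outcome and the sample size are not affected.

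**Working it through.** **1. The plan's own figure.** The SAP's only calculation is the sample size for closure of 60% (dHACM) against 90% (HPTC):

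n = (1.96 + 0.84)² × [0.6 × 0.4 + 0.9 × 0.1] / 0.3² = 7.84 × 0.33 / 0.09 = 28.75, so 29 per group, rounded up to 30. This reproduces and is not in dispute. The two rates and n = 30 are the inputs below.

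**2. Range of scar age.** With closure first recorded at weekly visits 1 to 6, scar age at Week 6 is 6 − k for closure at visit k, which gives 5, 4, 3, 2, 1 or 0 weeks. At the Week 7 follow-up it is 1 to 6 weeks.

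**3. Mean gap in scar age between arms.** The documents give no closure-time curve. Assume Weibull closure times with S(t) = exp[−(st)^c], and s set in each arm so that 60% or 90% have closed by Week 6. The mean scar age at Week 6 among closed ulcers is Σ(6 − k)[S(k−1) − S(k)] / [1 − S(6)].

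| Shape c (assumed) | dHACM, weeks | HPTC, weeks | Gap, weeks |
|---|---|---|---|
| 0.7 | 3.43 | 3.99 | 0.55 |
| 1 (constant hazard) | 2.94 | 3.53 | 0.59 |
| 2 | 1.89 | 2.40 | 0.52 |
| 3 | 1.33 | 1.75 | 0.42 |

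(Gaps are taken before rounding.) At Week 7 every age is one week greater and the gaps are unchanged. Under constant hazard the gap is smaller at earlier visits: 0 at Week 1, 0.06 at Week 2 and 0.27 at Week 4. The SD of scar age between patients within an arm is 1.67 weeks (dHACM) and 1.50 weeks (HPTC), so most of the variation is between patients and not between arms.

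**4. Number rated.** If 60% and 90% are Week 6 rates, 30 × 0.60 = 18 and 30 × 0.90 = 27 patients have a closed ulcer to score; 12 and 3 do not.

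**5. Size of the selection effect.** Assume that ease of healing is standard normal in both arms, that the easiest 60% or 90% close, and that ease correlates with a better scar at r. Assume no difference in scar quality between products. The mean of the top fraction p is φ(z_p)/p:

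- p = 0.60: 0.3863 / 0.60 = 0.644
- p = 0.90: 0.1755 / 0.90 = 0.195
- difference: 0.644 − 0.195 = 0.449 SD

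Multiplying by r gives 0.13 SD (r = 0.3), 0.22 SD (r = 0.5) and 0.31 SD (r = 0.7), all against HPTC.

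**6. Against sampling error.** The standard error of a difference in means with 18 and 27 scored is √(1/18 + 1/27) = 0.30 SD. A spurious 0.22 SD is below one standard error and would give p < 0.05 in about 11% of t-tests.

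**The case against.** The strongest reply is that the scar score is the last of the listed outcomes, that its five items do rate appearance, and that the plan never commits to a t-test of it at a given visit. All of that is true. It limits the weight of the point without removing it: the general rules are the only analysis available, and none of them accounts for time since closure or for who has healed.

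Several stronger readings are tempting and are not supported.

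- **That the score measures closure time and not scar quality.** Neither document shows how fast the score changes over the first weeks. Scar age is an uncontrolled influence of unknown strength.
- **That the faster product's scars are older at every visit.** The SAP assumes a higher proportion closed, not a speed. The early gaps are close to nil, and the direction can reverse. Suppose both arms close 10% per week to Week 4, and then HPTC closes 25% per week against 10%. The totals are 90% and 60%, but the mean scar age at Week 6 is (0.1 × 14 + 0.25 × 1)/0.9 = 1.8 weeks for HPTC against 15/6 = 2.5 for dHACM.
- **That the 0-to-5-week range is a bias.** It is a range between patients. The between-arm gap is what biases the comparison, and it is modest.
- **That partly healed skin is scored.** The outcome's title refers to the healed wound. The fair criticism is that scoring of open ulcers is undefined.
- **That 18 and 27 are the SAP's own counts.** The SAP attaches no time point to 60% and 90%.

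**Conclusion.** The point holds as a minor one. Scores are taken by calendar visit without reference to closure, so scar age at Week 6 can differ by up to 5 weeks between patients and is confounded with treatment if closure is faster in one arm. The mean gap is about 0.4 to 0.6 week under the assumed curves, and its effect on the score cannot be sized from the documents.

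The firmer part is selection: a test among healed ulcers does not compare randomised groups, whatever is believed about how scars mature. Its size, 0.13 to 0.31 SD against HPTC, rests on the assumed correlation of 0.3 to 0.7, on the latent-ease model and on 60% and 90% applying at Week 6. It is about one standard error or less, so it is unlikely by itself to produce a significant result, but it is large enough that the comparison should not be presented as a product effect on scar quality.

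Separately, and without any assumption, the outcome definition (every visit) and the Data Collection list (Week 6 only) disagree on when scars are scored.

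**What to change.** 1. Reconcile the outcome definition with Data Collection and Monitoring items b and d, so that both documents give one schedule for scar scoring.
2. State that only fully closed ulcers are scored, using the closure definition already in secondary outcome ii.
3. Use the score at the visit one week after first recorded closure. Every closure up to Week 6 then fits within the 7-week window, and scar age is equal to within the visit interval.
4. Report the score by arm as descriptive, with the number closed and the closure week beside it, and do not present it as a tested product effect.
5. If scores turn out to exist only at Week 6, the anchored score cannot be derived. Report the Week 6 scores descriptively with closure week.

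Anchoring deals with scar age but not with selection, which is why item 4 is needed. An alternative that keeps all randomised patients is a rank test with unclosed ulcers placed below any scar. It should not serve as the scar outcome. With 30 per arm, closure of 60% and 90% and no difference in scar quality, it gives p < 0.05 in about 53% of simulated trials, in favour of HPTC, so it mostly repeats the closure-proportion outcome.

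**Cost.** This is a change of wording in the outcome and the SAP, with no new assessments if scores are taken at each visit as the outcome definition says. Closure week is already needed for the Kaplan-Meier analysis. There are two small drawbacks: ulcers closing at Week 6 must be scored at the one-week follow-up, and the result describes early scar appearance only.

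### Pain and Wound-QoL are defined as change, but neither document lists a pre-treatment score or says what change is measured from

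*Protocol*

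**What the plan says.** Under Other Pre-specified Outcome Measures, the protocol defines item i as "change in pain measured by a Visual Analog Scale with score range from 0 to 10" and item ii as "change in quality of life assessed using the Wound-QoL questionnaire", which has 17 questions. Both carry the entry "Time Frame: 7 weeks including 1-week follow-up". For pain it adds "Pain scores were assessed weekly". Neither item says from which day change is counted.

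The Data Collection and Monitoring section, repeated in the SAP, sets out the schedule:

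- Item a: "Baseline data: Demographics, medical history, ulcer characteristics".
- Item b, weekly follow-ups: wound measurements, then "assess healing progress, pain scores, record adverse events and patient-reported outcomes".
- Item c: histology specimens at baseline and day 5.
- Item d: "End-of-Study Visit (Week 6): final wound assessment, collect patient feedback on treatment experience, quality of life and scar assessment".

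The SAP's Data Analysis section gives Student's t-test for continuous variables. It has no definition of change and no adjustment for a starting value.

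**The concern.** A change score needs a starting value. For a treatment comparison, that value has to precede treatment. The written schedule does not supply one for either instrument. A site that followed it literally would record the first pain score at the first weekly follow-up. By then the wound has been debrided, the product applied, and a second punch biopsy taken on Day 5.

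A change counted from that point measures only what happens after the first week. Any difference between the products that has already appeared is absorbed into the reference and removed from the comparison. The trial is also open-label, so a first score taken after application could carry the patient's expectation of the product as well as its early effect.

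The protocol's introduction states patient-reported outcomes as part of the trial's aim. Pain and Wound-QoL are the named instruments that serve it.

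**Working it through.** **1. Schedule, item by item**

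| Measure | Listed at baseline? | First listed |
|---|---|---|
| Histology | Yes (item c; also before application, under secondary outcome i) | Baseline |
| Pain VAS | No | Weekly follow-ups (item b) |
| Wound-QoL | No | Named at no visit; quality of life appears only at Week 6 (item d), and item b's patient-reported outcomes may or may not include it |

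Histology is the only outcome assessment that the section explicitly schedules both at baseline and after treatment. The primary outcome counts its weeks from week 1. On a literal reading the first weekly follow-up is therefore at about day 7, two days after the Day-5 biopsy. For Wound-QoL, the narrowest reading leaves a single time point, and no change can be formed.

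**2. The plan's own figure**

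The only computed design figure is the SAP's sample size for complete closure:

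(1.96 + 0.84)² × [0.6(0.4) + 0.9(0.1)] / 0.3² = 7.84 × 0.33 / 0.09 = 28.75

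This gives 29 per group, with 30 used, so the figure reproduces. It does not concern pain or quality of life. Only the 30 per arm is carried forward.

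**3. Illustration: change counted from Week 1**

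The documents give no SD, effect or correlation for either instrument, so everything here except the 30 per arm, the two-sided 5% level and the 80% power is assumed. Work in SD units of a single score. Let f be the share of the between-arm effect already present at Week 1, and r the correlation between two scores of the same patient.

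- SE of a difference in means of single scores: √(2/30) = 0.258.
- Effect detectable with 80% power from one post-treatment score: (1.96 + 0.84) × 0.258 = 0.72 SD.
- SE of a difference in mean change: 0.258 × √(2(1 − r)). At r = 0.5 this is again 0.258.
- Effect visible in change from Week 1: 0.72 × (1 − f).
- Power: Φ(0.72(1 − f)/SE − 1.96).

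For r = 0.5 and f = 50%: 0.362/0.258 − 1.96 = −0.56, and Φ(−0.56) = 29%. The range over both assumptions is:

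| r | f = 0 | f = 25% | f = 50% | f = 75% |
|---|---|---|---|---|
| 0.3 | 66% | 43% | 22% | 9% |
| 0.5 | 80% | 56% | 29% | 10% |
| 0.7 | 95% | 77% | 44% | 15% |

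The f = 0 column is also the power of change from a true Day-0 score with the same r.

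**4. What a Day-0 score would buy**

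The detectable difference at 80% power, 30 per arm, in SD:

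| Analysis | r = 0.3 | r = 0.5 | r = 0.7 |
|---|---|---|---|
| Post-treatment level only, 0.72 | 0.72 | 0.72 | 0.72 |
| Change from Day 0, 0.72 × √(2(1 − r)) | 0.86 | 0.72 | 0.56 |
| ANCOVA on Day 0, 0.72 × √(1 − r²) | 0.69 | 0.63 | 0.52 |

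ANCOVA gives the smallest detectable difference in every column. An unadjusted change score is worse than the post-treatment level alone when r is below 0.5.

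**The case against.** The strongest reply is that absence from item a does not prove absence at baseline. That list is plainly not exhaustive. Wound area and ankle-brachial index must be known before treatment, because eligibility depends on them, and neither is named there. Weekly assessment does not exclude Day 0, and the word change suggests that a starting value was intended.

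This stands as far as it goes. A reader might infer that the first pain and Wound-QoL scores were in fact taken after a week of treatment. The documents do not establish that. It is an inference from list headings, and for Wound-QoL a Week 1 score is only one reading. The reply does not supply what is missing, however. Eligibility forces a pre-treatment wound area, and histology is explicitly scheduled at baseline. Nothing does either for pain or Wound-QoL, and no reading yields a stated reference value.

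A second reply is that randomisation protects the comparison. This is right for levels: comparing post-treatment scores between arms is unbiased with no baseline at all. Chance imbalance in starting pain is a loss of precision that the standard error already reflects, and it should not be described as hidden bias. The subtraction problem arises only if change is taken from a treated value.

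Two further inferences should be resisted. These are not the only patient-reported data, since patient feedback on treatment experience is also collected at Week 6. The lack of a minimum pain score at entry is not a fault here: recognising low pain needs a baseline score, not an entry threshold.

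**Conclusion.** The point holds as a gap in the plan: two outcomes defined as change, no pre-treatment score listed for either, and no reference value defined in either document. Following the schedule as written would give change from a treated value for pain. For quality of life it would give either the same or no computable change. Whether that happened cannot be told from the text.

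The size is conditional. If change is counted from Week 1, the share of the effect present by then is lost. At r = 0.5 and a true effect of 0.72 SD, power falls from 80% to 56%, 29% or 10% for shares of 25%, 50% or 75%. Across r from 0.3 to 0.7, a 50% share leaves 22% to 44%. The effect, shares and correlations are assumptions, so these figures show how the loss grows and do not estimate what occurred in this trial.

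The consequence is limited to other pre-specified outcomes. It should be corrected because the remedy is simple and patient-reported outcomes are a stated aim.

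**What to change.** 1. In both documents, add the pain VAS and the 17-item Wound-QoL to the baseline data, completed on Day 0 before debridement, biopsy and application.
2. Name Wound-QoL at each visit where it is collected, so that the weekly reference to patient-reported outcomes is unambiguous.
3. Define change as the score at each visit minus the Day-0 score.
4. In the SAP's Data Analysis section, compare arms on these outcomes by ANCOVA with the Day-0 score as covariate, in place of the unadjusted t-test.

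The cost is a few minutes of patient time at an existing visit and a short edit to each document.

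The text is written largely in the past tense, so enrolment may be complete. In that case, state whether and when a pre-application score was taken. If one exists, apply items 3 and 4. If none exists, report pain and Wound-QoL as levels, compare them between arms at the post-treatment visits, and make no claim about change from pre-treatment. That comparison remains unbiased under randomisation. It gives up only the precision that adjustment would have added: a detectable difference of 0.72 SD instead of 0.69 to 0.52 SD for r from 0.3 to 0.7.

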Title: A RCT Evaluating Efficacy of Type-I Collagen Skin Substitute vs. Human Amnion Membrane in Treatment of Venous Leg Ulcers

NCT No: NCT06831760

Date: July 8, 2025

Study Aims

This randomized, controlled clinical trial aimed to compare clinical efficacy, healing outcomes, of High Purity Type-I Collagen Skin Substitute (HPTC) vs. Dehydrated Human Amnion / Chorion Membrane (dHACM) in the treatment of venous leg ulcers.

Sample Size Calculation

Standard Two-Sample Comparison of Proportions (e.g., wound closure rate)

Assuming:

- $\alpha = 0.05$ (5%)
- **Power** = 0.80 (80%)
- **Proportion of success in control (p_1)** = 0.60 (typical healing rate for dHACM)
- **Proportion of success in treatment (p_2)** = 0.90 (expected improvement with Type-I collagen)

We use the formula for comparing two proportions:

$$n = (p_1 - p_2)^2 (Z\alpha/2 + Z\beta)^2 / [p_1(1 - p_1) + p_2(1 - p_2)]$$

Where:

- $Z\alpha/2 = 1.96$ for $\alpha = 0.05$
- $Z\beta = 0.84$ for 80% power

$$n = (1.96 + 0.84)^2 \cdot [0.6(0.4) + 0.9(0.1)] / (0.9 - 0.6)^2 = 7.84 \cdot [0.24 + 0.09] / 0.09 = 7.84 \cdot 0.33 / 0.09 = 2.59 / 0.09 \approx 28.8$$

We use the formula for comparing two proportions:

$$n = \frac{(Z_{\alpha/2} + Z_{\beta})^2 \cdot [p_1(1 - p_1) + p_2(1 - p_2)]}{(p_1 - p_2)^2}$$

Where:

- $Z_{\alpha/2} = 1.96$ for $\alpha = 0.05$
- $Z_{\beta} = 0.84$ for 80% power

$$n = \frac{(1.96 + 0.84)^2 \cdot [0.6(0.4) + 0.9(0.1)]}{(0.9 - 0.6)^2} = \frac{7.84 \cdot [0.24 + 0.09]}{0.09} = \frac{7.84 \cdot 0.33}{0.09} = \frac{2.59}{0.09} \approx 28.8$$

~29 participants per group - 30 per group is statistically adequate to detect a difference from 60% to 90% healing rate with 80% power.

Randomization and Blinding: Patients were randomized 1:1 to the HPTC or dHCAM group using a computer-generated randomization sequence. Open-label design (patients and clinicians were aware of treatment allocation). Outcome assessors and statisticians were blinded.

Data Collection and Monitoring

- a. Baseline data: Demographics, medical history, ulcer characteristics.
- b. Weekly follow-ups: Wound measurements (photographic documentation), assess healing progress, pain scores, record adverse events and patient-reported outcomes.
- c. Histopathological specimens were obtained at baseline and day 5 for vascularity assessment.
- d. End-of-Study Visit (Week 6): final wound assessment, collect patient feedback on treatment experience, quality of life and scar assessment.
- e. Data entry and monitoring was managed using an electronic data capture system.

Data Analysis: Data was analysed using SPSS v26.0. Continuous variables were expressed as mean \pm standard deviation, and categorical variables as frequencies and percentages. Student's t-test was used for comparing continuous variables between groups, and chi-square test for categorical variables. A p-value <0.05 was considered statistically significant. Kaplan-Meier survival analysis was used to assess time to complete healing and Cohen's d values for primary histopathological parameters.

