Sixty patients aged 18–80 years with non-infected chronic venous ulcers of more than 4 weeks' duration, measuring between 2 cm² and 25 cm², with adequate arterial inflow (Ankle Brachial Index > 0.8) and willingness to comply with follow-up were included. Exclusion criteria included active infection requiring systemic antibiotics, uncontrolled diabetes, peripheral arterial disease, autoimmune disorders, malignancy, immunosuppression, pregnancy and known allergies to bovine or human-derived products. Patients were randomly allocated into two equal groups using a computer-generated sequence:

- Group A: Treated with High Purity Type-1 collagen-based skin substitute (HPTC) (n=30)
- Group B: Treated with dHACM (n=30)

Intervention: Application protocols followed manufacturer instructions. Wounds were debrided before initial grafting. All patients received standard wound cleaning and compression therapy. In addition:

- Group A received application of HPTC, a high-purity Type-I collagen dressing. The product was sized to cover the entire wound surface with a 1-cm margin and secured with appropriate secondary dressings
- Group B received dHACM graft. The membrane was rehydrated and applied to cover the wound bed completely
- Standard Wound Care for Both Groups - First layer of a non-adherent and porous paraffin gauze followed by Second layer of absorbent gauze pads and then third layer of a soft roll and crepe bandage.

Infection control measures were taken and patient education regarding wound care and leg elevation were given. Repeat application was done if deemed necessary.

Outcome Measures:

Primary Outcome Measure:

- i. Percentage wound area reduction - percentage wound area reduction from week 1 through week 6 plus 1 week follow up measured manually with digital photography

Secondary Outcome Measure:

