- i. **Infiltration of vascularity in the ulcer bed** - Infiltration of vascularity in the ulcer bed on day 5 of application. Vascularity assessment will be done using biopsy on Day 0 of application to be compared with Day 5 after application of Type-I Collagen-based Skin Substitute or Human Amnion/Chorion Membrane. [Time Frame: 6 days]. Histopathological Assessment – Before application and on the 5th day post-application of either HPTC or dHCAM, a 2mm punch biopsy was obtained from the wound edge extending into the wound bed under local anaesthesia (2% lidocaine without epinephrine). Biopsy samples were immediately fixed in 10% neutral buffered formalin for 24 hours, processed through graded alcohols, and embedded in paraffin blocks. Serial sections of 4 μ m thickness were prepared and stained with:
 - i. Hematoxylin and Eosin (H&E) for general morphology
 - ii. Masson's Trichrome for collagen assessment
 - iii. CD31 immunohistochemistry for capillary density evaluation
 - iv. α -SMA immunohistochemistry for fibroblast activity

Histological Parameters Evaluated

1. Vascular Infiltration: Assessed by counting new blood vessels per High Power Field (hpf) **(0-3 scale)**
 - 0: Minimal vascular ingrowth (<5 vessels/hpf)
 - 1: Mild infiltration (5-10 vessels/hpf)
 - 2: Moderate infiltration (11-20 vessels/hpf)
 - 3: Abundant infiltration (>20 vessels/hpf)
2. Neo-epithelialization: Measured as epithelial migration distance from wound edge **(0-3 scale)**
 - 0: No epithelial migration
 - 1: Minimal migration (<25% wound coverage)
 - 2: Moderate migration (25-75% coverage)
 - 3: Extensive migration (>75% coverage)

3. Fibroblast Activity: Quantified by counting α -SMA positive fibroblasts per HPF and assessment of fibroblast morphology (**0-3 scale**)
 - 0: Sparse, inactive fibroblasts
 - 1: Moderate cellularity, minimal matrix production
 - 2: High cellularity, active-matrix synthesis
 - 3: Very high activity with extensive matrix deposition
4. Capillary Density: Evaluated using CD31 staining, counted as vessels per mm^2 of tissue
5. Inflammatory Response: Graded semi-quantitatively (**0-3 scale**)
 - 0: Minimal inflammatory infiltrate
 - 1: Mild chronic inflammation
 - 2: Moderate mixed inflammation
 - 3: Severe acute inflammation
6. Collagen Deposition: Assessed using Masson's Trichrome staining (**0-3 scale**)
 - 0: Minimal collagen matrix
 - 1: Loose, immature collagen
 - 2: Moderate organized collagen
 - 3: Dense, mature collagen architecture

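### The t-test on percentage wound area reduction ignores baseline ulcer area, which is already measured; one covariate would add precision if size still predicts percentage healing

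*SAP*

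**What the plan says.** The SAP's Data Analysis section gives one rule for continuous outcomes: Student's "t-test was used for comparing continuous variables between groups, and chi-square test for categorical variables". Kaplan-Meier is reserved for time to complete healing. Neither document mentions ANCOVA, regression, a covariate or a stratification factor.

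The Protocol's primary outcome is "percentage wound area reduction from week 1 through week 6 plus 1 week follow up measured manually with digital photography". It is continuous, so the t-test applies to it through the general rule; the SAP does not name a test for the primary outcome as such.

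Baseline size is available. Ulcers enter the trial "measuring between 2 cm² and 25 cm²", the Data Collection and Monitoring list (in both documents) begins with "Baseline data: Demographics, medical history, ulcer characteristics", and a percentage reduction cannot be computed without a starting area. On allocation the SAP says that "Patients were randomized 1:1 to the HPTC or dHCAM group using a computer-generated randomization sequence".

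Baseline values matter for other outcomes too. For vascularity the Protocol states that "Vascularity assessment will be done using biopsy on Day 0 of application to be compared with Day 5", and pain and Wound-QoL are defined as change. No analysis is described that uses a baseline value as a covariate.

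**The concern.** Dividing by starting area removes the influence of size only if ulcers shrink in proportion to their area. If healing instead advances inwards from the edge at some rate per week (an assumption, though the Protocol's histology does measure epithelial migration from the wound edge), a small ulcer loses a larger percentage than a large one in the same time. The entry range is 12.5-fold in area (25/2), so the leftover dependence need not be trivial.

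An unadjusted t-test leaves that variation in the residual. With 30 per arm and no size stratification described, the confidence interval is wider than it need be, and any chance imbalance in ulcer size stays in the estimate. The sample size was set on closure proportions, and no SD, expected difference or power is given for the primary outcome, so its precision has not been planned for in any other way.

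**Working it through.** **1. The plan's own figure.** From the SAP's Sample Size Calculation: (1.96 + 0.84)² × (0.24 + 0.09) / 0.09 = 7.84 × 0.33 / 0.09 = 28.75, which agrees with the stated 28.8, or 29 per group, with 30 used. This concerns closure (60% vs 90%), not percentage area reduction, so the reference difference for the primary outcome has to be set separately.

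**2. Reference difference.** A two-sided 5% t-test with 30 per arm (58 df, noncentral t) has 80% power at a difference of 0.736 SD.

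**3. Adding one covariate.** Let r be the within-arm correlation between log baseline area and the outcome. The residual variance becomes (1 − r²) of the original. Chance imbalance in the covariate inflates the variance by about 1 + 1/56 = 1.018, and 57 df remain. The noncentrality is 0.736 × √(30/2) / √[1.018 × (1 − r²)].

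| r (assumed) | Net variance ratio | Effective n per arm, 30/(1 − r²) | ANCOVA power |
|---|---|---|---|
| 0 | 1.018 | 30.0 | 79.3% |
| 0.2 | 0.977 | 31.2 | 80.9% |
| 0.3 | 0.926 | 33.0 | 82.9% |
| 0.4 | 0.855 | 35.7 | 85.7% |
| 0.5 | 0.763 | 40.0 | 89.4% |

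Break-even is where 1.018 × (1 − r²) = 1, that is |r| ≈ 0.13. Simulation of the same setting gives 80.2% (t-test) vs 79.5% (ANCOVA) at r = 0, 80.7% vs 83.5% at 0.3, and 80.6% vs 89.3% at 0.5.

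**4. With the ceiling at 100%.** The table above assumes an unbounded outcome, whereas the SAP expects 60% and 90% of ulcers to close, so many values would sit at exactly 100%. To allow for this, assume circular ulcers of radius r₀ = √(A/π) and an edge advancing v cm per week for 6 weeks:

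reduction = 100 × [1 − max(0, 1 − 6v/r₀)²].

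Here v is log-normal with log-SD 0.4 or 0.7, areas are uniform or log-uniform on 2 to 25 cm², and the median v is solved to give 60% and 90% closure (control 0.289 to 0.391 cm/week). Each setting uses 20,000 simulated trials.

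| Areas | Log-SD of v | Power gain from ANCOVA (points) |
|---|---|---|
| Uniform | 0.4 | 2.6 |
| Uniform | 0.7 | 1.0 |
| Log-uniform | 0.4 | 6.3 |
| Log-uniform | 0.7 | 2.8 |

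Across the four settings:
- Control-arm r is −0.26 to −0.48. Mean control reduction is 99–100% for a 2 cm² ulcer and 80–90% for a 25 cm² ulcer.
- Power is 65–69% unadjusted and 68–75% adjusted.
- The variance of the estimate falls by 2–13%.
- Type I error is 4.6–4.9% unadjusted and 4.6–5.0% adjusted.

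A different ceiling model (a normal outcome capped so that 60% of controls are fully closed, with a larger assumed effect) gives 68.7% vs 69.5% at latent r = 0.3 and 70.0% vs 74.8% at latent r = 0.5.

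**5. Chance imbalance.** The difference in mean log area between arms has SD √(2/30) = 0.258 in SD units. P(|imbalance| ≥ 0.5 SD) = 2 × P(Z > 0.5/0.258) = 5.3%. At r = 0.3, a 0.5 SD imbalance moves the unadjusted estimate by 0.3 × 0.5 = 0.15 SD, and 0.15/0.736 = 20% of the detectable difference.

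**6. Outcomes with a baseline value.** With equal SDs (assumed), the variance of a change score is proportional to 2(1 − r) and that of ANCOVA to 1 − r², where r is now the correlation between baseline and follow-up values of the same measure. This gives 1.40 vs 0.91 at r = 0.3, 1.00 vs 0.75 at r = 0.5, and 0.60 vs 0.51 at r = 0.7.

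**The case against.** The strongest reply is that nothing here is an error. An unadjusted t-test in a 1:1 randomised trial is a legitimate choice, the endpoint already divides by starting size, and no figure in the documents shows that r exceeds 0.13. All of that is true, and it is why the point is one of efficiency and its size is conditional.

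Three further objections limit the benefit:
- **Ceiling.** With most ulcers expected to close, the unbounded power series overstates the gain. In the edge model, three of four settings gain less than 3 points; the 6.3 needs log-uniform areas and the smaller spread of healing rates together.
- **Unequal arms.** In that same model the HPTC-arm correlation is only −0.13 to −0.24, the pooled within-arm correlation averages −0.20 to −0.38, and the outcome SDs differ about threefold (control 8–15, HPTC 3–5). A common-slope, equal-variance ANCOVA is therefore an approximation. It is not harmful: adjusted power was higher in every setting, and the power figures already include these features. The type I error figures come from simulations in which the two arms have the same distribution, so they do not test unequal variances; with equal arm sizes, though, the pooled standard error is little affected by them.
- **A larger loss elsewhere.** An unadjusted Mann-Whitney test has about 81–82% power in this model, more than either linear analysis. It answers a different question from a difference in means, so it is a separate decision, but it shows that the ceiling costs more power than the missing covariate.

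It is also fair that chance imbalance is already reflected in the t-test's standard error. Adjustment removes the imbalance from the particular estimate; it does not repair a bias. Finally, the SAP is written in the past tense ("Data was analysed using SPSS v26.0"), so it may be too late for the primary analysis to change.

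**Conclusion.** The point holds as a conditional efficiency issue; it is not a validity error. The plan omits a baseline measurement that it necessarily has, and including it adds precision whenever |r| exceeds about 0.13. The trade is asymmetric: a loss of about 0.7 power points if r is near 0, against gains of 2.9 points at r = 0.3 and 9.4 at r = 0.5 for an unbounded outcome. Once the ceiling at full closure is allowed for, about 1 to 6 points is the more realistic expectation.

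These sizes rest on assumed correlations and, for the last range, on an assumed edge-advance model calibrated to the SAP's closure rates. The change is worth making because it is nearly free. Confidence in its size is medium. It does not alter the stated 30 per group, which was derived for closure.

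**What to change.** State one primary model in the SAP: linear ANCOVA of percentage wound area reduction at week 6 on treatment and log baseline ulcer area, two-sided 5%, with the unadjusted t-test as a sensitivity analysis. Week 6 is suggested because both documents list "End-of-Study Visit (Week 6): final wound assessment"; the primary outcome definition names a span of weeks, so the SAP must fix the single time point.

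Use the Day 0 value as covariate for Day 5 capillary density. For pain and Wound-QoL, use the baseline value where one is recorded; the baseline data list does not name either, so this needs confirming.

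If outcome data have already been seen, keep the t-test as the planned analysis and report the adjusted model labelled as post hoc.

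Cost: one SAP sentence for the primary outcome, no new data, no change in sample size and one degree of freedom. If the data are already unblinded, the benefit is limited to the labelled post hoc analysis.
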